3.7 Criteria for Removal from the Study

Subjects will be removed from the study if any of the following occur:

- a. Patient request for removal.
- b. Primary physician request for removal.
- c. Surgical complication such as infection, bleeding, organ failure, or mechanical bowel obstruction.
- d. Development of skin changes at the acustimulation sites during the period of treatment.

3.8 Statistical considerations:

Analysis Methods:

The primary aim of this study is to examine the efficacy of electrical stimulation of P6 combined with prophylactic antiemetics versus pharmacological prophylaxis alone in preventing the incidence of PONV following breast surgery in patients at high-risk for PONV. We will make a preliminary evaluation of efficacy by testing for a difference in incidence of PONV between study arms. If a subject fails to have complete control of nausea (as defined in Section 3.5) at any time during her PACU stay, she will be considered as having PONV. We will use a 1-sided chi-squared test of proportions with Type I error of 0.1 to test for difference in PONV incidence.

Secondary endpoints of interest are feasibility of the study, use of rescue anti-emetic medications, post-operative patient satisfaction, PACU length-of-stay, hospital admission, and patient expectations. We will calculate rates, frequencies, and 90% confidence intervals (CIs), as applicable, and will judge the trial feasible if at least 20% of screened patients meet inclusion criteria, 50% of patients who meet the inclusion criteria consent, and 75% of patients within the acupuncture arm complete all procedures. We will also calculate the appropriate summary statistics and 90% CIs for other secondary endpoints by group, as well as for differences between groups. We will evaluate preliminary differences in the severity of PONV and use of rescue anti-emetic medications between groups using mixed model analyses. Additionally, we will explore associations between genetic polymorphisms in COMT, 5HT3, OPRM1, and DRD2 and response to P6 stimulation using ANOVA models with factors such as the number of matching alleles and treatment group. Finally, we will tabulate and compare adverse events by study arm.

Sample size calculations:

This study is powered for a preliminary examination of efficacy in order to determine whether there is early evidence of efficacy to justify moving forward with further studies of intra-operative NMBM stimulation of P6 to prevent PONV. Similar studies in other patient populations in which pharmacological prophylaxis was used with or without acupoint stimulation found that incidence of PONV was approximately 0.4 in the control group and 0.25 in the experimental group.[17-20] To test whether a similar difference exists in this patient population, we will need 88 patients per arm to achieve 80% power when using a 1-sided chi-squared test with $\alpha = 0.1$. With regard to the secondary objective of feasibility evaluation, to achieve a sample size of 88 per arm, assuming 20% of screened patients meet the inclusion criteria and of those patients, 50% consent, we would need to screen 1,760 potential subjects to obtain 352 eligible subjects, and of these, 176 would consent to be in the study. Under these circumstances, the half-width for a 90% confidence interval regarding inclusion criteria would be 0.016 and the half-width for a 90% confidence interval regarding consent would be 0.044. If 75% of the subjects within the acupuncture arm complete the study, the 90% confidence interval around this statistic would be 0.076 with N=88 for the acupuncture arm.

Missing Data:

Given a patient's active involvement only lasts until discharge from PACU, we do not expect to have issues with missing data and drop-outs, and our primary analyses will be based on observed data. Should we find that missing data and/or drop-outs become an issue ($> 10\%$ in either arm), we will conduct additional sensitivity analyses using approaches including multiple imputation, pattern-mixture models, and selection models to account for potential missing-at-random or missing-not-at-random mechanisms.[43] The primary along with the sensitivity analyses will provide a comprehensive assessment of the effects of interest, and similar results based on these analyses would strengthen our preliminary study findings.

Interim Analysis:

No formal interim analyses are planned, however, we will present aggregate efficacy and safety data to the MDACC DSMB so that they can assess whether enrollment should halt for futility or toxicity reasons. In addition to summary statistics, we will also calculate $\Pr[\pi_{IES} < \pi_{SOC} \mid \text{data}]$, where π_{IES} and π_{SOC} are the proportions of women who report complete control of nausea (as defined in Section 3.5 of the protocol) at any time during the PACU stay in the electrical stimulation arm and control arm, respectively. This probability will

also be presented in the DSMB report to assess whether enrollment should continue in the trial. When calculating this probability, we will assume that both π_{IES} and π_{SOC} have a prior beta distribution with $\alpha = 0.8$ and $\beta = 1.2$. In addition, we will examine the defined feasibility criteria during the annual DSMB report. If the results look sufficiently clear that feasibility is not achieved, we will consider terminating the study, provided that the DSMB recommends so.

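### The DSMB probability is defined on complete control, so as written it is the chance that stimulation is worse, while its prior, inequality sign and wording fit PONV incidence

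*Combined protocol and SAP*

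**What the plan says.** Section 3.8, Interim Analysis, plans no formal interim analysis. Aggregate efficacy and safety data go to the DSMB "so that they can assess whether enrollment should halt for futility or toxicity reasons". Besides summary statistics, the report contains Pr[π_IES < π_SOC | data], which will "also be presented in the DSMB report to assess whether enrollment should continue in the trial". For each arm, stimulation and control, the parameter is defined over the time in the PACU by this phrase: "proportions of women who report complete control of nausea (as defined in Section 3.5 of the protocol) at any time". For the prior, "we will assume that both π_{IES} and π_{SOC} have a prior beta distribution with" parameters 0.8 and 1.2. The section gives no cut-off and does not say whether a high or a low value argues for stopping.

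Three other places bear on this:

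- Section 3.5, item 1, defines complete control as a favourable state over the PACU stay: no nausea score of 3 or more, no vomiting and no anti-emetic use.
- Section 3.8, Analysis Methods, defines the primary event as its complement. "If a subject fails to have complete control of nausea (as defined in Section 3.5) at any time during her PACU stay", she counts as having PONV.
- Section 3.8, Sample size calculations, takes from similar studies that "incidence of PONV was approximately 0.4 in the control group and 0.25 in the experimental group".

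**The concern.** The outcome named for π is a good one, but the other parts of the definition fit the bad one.

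- **Inequality.** A lower proportion under stimulation means benefit only if the proportion counts PONV. For complete control it means harm.
- **Prior.** A mean of 0.40 matches the planned control PONV rate and neither planned complete-control rate.
- **Phrase *at any time*.** In Analysis Methods it is attached to failure of control, where it makes sense: one failure during the stay is enough. In Interim Analysis the same phrase appears without the failure, attached to a state that section 3.5 defines over the whole stay.

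The likeliest explanation is that the failure was dropped from the sentence. The number is meant to inform whether enrolment continues. A DSMB that reads the inequality as benefit would see a low value for a treatment performing as planned, and a high value for one that is equally worse. There is also a programming risk. One analyst could code the words and another the evident intent, and their reports would point in opposite directions.

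**Working it through.** **Inputs.** Planned PONV is 0.40 (control) and 0.25 (stimulation), from Sample size calculations. Since PONV is failure of complete control, planned complete control is 1 − 0.40 = 0.60 and 1 − 0.25 = 0.75. The prior is Beta(0.8, 1.2) for both arms, from Interim Analysis. The documents give no numerical value for the DSMB probability and no interim sample size. The looks at 20, 44 and 88 per arm below are assumptions; 88 is full accrual.

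**Step 1: the plan's own figure.** For a 1-sided test with α = 0.1, 80% power, pooled variance under the null and no continuity correction:

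n = [1.2816·√(2 × 0.325 × 0.675) + 0.8416·√(0.40 × 0.60 + 0.25 × 0.75)]² / 0.15² = (0.849 + 0.550)² / 0.0225 = 87.01

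This rounds up to 88 per arm, as stated. The planning rates are therefore PONV rates, with lower meaning better.

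**Step 2: the prior.** Mean = 0.8 / (0.8 + 1.2) = 0.40, with the weight of 2 patients. The mirrored prior for complete control is Beta(1.2, 0.8), with mean 0.60.

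**Step 3: the probability.** With x women out of n having the outcome, each arm's posterior is Beta(0.8 + x, 1.2 + n − x), and

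Pr[π_IES < π_SOC | data] = ∫ F_IES(t) f_SOC(t) dt, by numerical integration.

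Example at 44 per arm. PONV counts nearest the planning rates are 11 and 18, so complete control is 33 and 26.

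- As written: Beta(33.8, 12.2) against Beta(26.8, 19.2), giving 0.059.
- On PONV: Beta(11.8, 34.2) against Beta(18.8, 27.2), giving 0.942.

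Hand check of the first: the posterior means are 33.8/46 = 0.735 and 26.8/46 = 0.583. The standard deviation of the difference is √(0.735 × 0.265/47 + 0.583 × 0.417/47) = 0.097, so z is about −1.58 and the normal approximation gives about 0.057.

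| Per arm (assumed look) | PONV counts, stimulation / control | As written | On PONV, same prior and sign | As written, rates swapped (stimulation worse) |
|---|---|---|---|---|
| 20 | 5 / 8 | 0.165 | 0.839 | 0.835 |
| 44 | 11 / 18 | 0.059 | 0.942 | 0.941 |
| 88 | 22 / 35 | 0.019 | 0.982 | 0.981 |

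With equal observed rates the value is 0.50.

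**Step 4: what drives the result.** Keeping complete control and the sign but using Beta(1.2, 0.8) moves the value only from 0.0590 to 0.0578 at 44 per arm, and from 0.0188 to 0.0184 at 88. The prior has almost no numerical effect. The reversal comes from the outcome label combined with the sign.

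**Step 5: sampling variation.** In trials simulated at the planning rates with 44 per arm, more than half of the values as written fall below 0.10 and more than nine in ten fall below 0.50.

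**The case against.** The strongest defence is that the stated purpose includes futility, and the probability that stimulation gives less complete control is a coherent futility measure: high is bad, low is reassuring. On that reading a working treatment should give a value near 0. This could explain the inequality. It does not explain a prior centred at 0.40 or the phrase *at any time*, and the text never states it. The prior is a clue to intent only.

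Other objections stand and limit the point:

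- A reader might infer that an interim rule runs backwards. It does not: there is no formal interim analysis and no threshold.
- A reader might take *at any time* literally and conclude that one good 15-minute reading is enough, so nearly every woman would qualify. The sentence cites section 3.5, whose definition covers the whole stay. Near-universal control in both arms would also put the probability near 0.5 (0.50 for 43/44 in each arm), not near 0.
- A reader might say this is the only comparative efficacy figure the DSMB sees. The documents do not establish that. Summary statistics also go to the DSMB; whether they are by arm is not stated, and if they are, the direction would be visible.
- The timing of any look is unknown. The section mentions an annual DSMB report, while section 3.2 expects accrual to finish in 10 months, so the first report could come after enrolment ends.

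**Conclusion.** The definition is inconsistent and should be corrected. As written, the quantity is the posterior probability that stimulation is worse, while the prior, the sign and the wording borrowed from the primary endpoint indicate that PONV incidence was meant. With data at the planning rates, the two readings differ by about 0.67 at 20 per arm (0.839 − 0.165), 0.88 at 44 (0.942 − 0.059) and 0.96 at 88 (0.982 − 0.019). How close to 0 the written version falls depends on accrual. These sizes rest on the assumed looks and on observed rates equal to the planning rates.

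The consequence is a risk of misreading or miscoding a number that informs whether enrolment continues. The documents do not support a claim that an effective treatment would be stopped. The primary chi-squared test and the 88 per arm are untouched.

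**What to change.** In section 3.8, Interim Analysis, use one of two equivalent definitions:

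1. Define π_IES and π_SOC as the proportions of women with PONV, meaning failure of complete control at any time during the PACU stay, as in Analysis Methods. Keep Beta(0.8, 1.2) and the inequality.
2. Keep complete control, stated as holding over the whole PACU stay, reverse the inequality to Pr[π_IES > π_SOC | data] and use Beta(1.2, 0.8).

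Both give identical values (at 44 per arm, 1 − 0.0578 = 0.9422). The first changes less and matches the primary endpoint. In either case add, in the plan and in the DSMB report, that values near 1 favour stimulation.

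The cost is one or two sentences, made before any DSMB report is produced. It needs no extra data or patients and leaves the primary analysis unchanged.
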